## 4.2 Exclusion criteria

Patients fulfilling any of the following criteria are not eligible for inclusion in this study. No additional exclusions may be applied by the investigator, in order to ensure that the study population will be representative of all eligible patients.

1. MGFA grade I, IVb, or V disease.
2. Documented presence of unresected thymoma.
3. Patients having undergone thymectomy or thymothymectomy (resection of thymoma) within 6 months of screening.
4. Patients having received any of the following treatments prior to randomization:
  - IVIg or plasma exchange within 8 weeks;
  - oral or IV cyclophosphamide treatment within 3 months;
  - IV corticosteroid bolus (dose higher than 1 mg/kg) within 3 months;
  - belimumab within 6 months. For patients who received belimumab earlier, B cell count should be within normal range;
  - rituximab within 12 months. For patients who received rituximab earlier, B cell count should be within normal range;
  - any other biologic or an investigational drug within 1 month or five times the half-life, whichever is longer.
5. Live vaccines within 4 weeks prior to randomization.
6. History of tumor, infection, or interstitial lung disease on chest CT, MRI, or CXR.
7. History of malignancy within 3 years prior to screening, with the exception of basal cell or squamous cell carcinoma of the skin or in situ carcinoma of the cervix.

8. History or presence of any medically significant cardiac condition which according to the investigator may jeopardize the patient in case of participation in the study including ischemic heart disease, congestive heart failure or cardiomyopathy, myocardial infarction or stroke.
9. Sitting vital signs outside of the following ranges at baseline: oral temperature: 35.0 - 37.5°C, systolic blood pressure: 90 - 145 mmHg, diastolic blood pressure: 50 - 90 mmHg, pulse rate 50 - 100 bpm.
10. Patients who are at significant risk for thromboembolic events as judged by the investigator or have any one of the following:
  - History of either thrombosis or 3 or more spontaneous abortions with or without the presence of anti-cardiolipin autoantibodies;
  - Presence of prolonged partial thromboplastin time (PTT).
11. Pancreatic injury or pancreatitis as indicated by abnormal signs or symptoms of pancreatitis or clinically significant elevations in amylase or lipase at screening.
12. Have had signs or symptoms of a clinically significant systemic viral, bacterial or fungal infection within 30 days prior to randomization.
13. Any significant concurrent medical condition such as pulmonary, renal or liver disease that, in the opinion of the principal Investigator, could affect the patient's ability to tolerate or complete the study.
14. Evidence of active or latent tuberculosis as assessed by quantiferon testing at screening (PPD is not recommended as immunosuppression may result in false negative result).
15. Positive serology for HIV antibodies, hepatitis B surface antigen or hepatitis C antibodies (confirmed by an appropriate licensed test) at screening.
16. Any of the following abnormal laboratory values at screening:
  - total white blood cell count (WBC) outside the range of 1,500-15,000/mm^3 (1.5-15.0 x 10^9/L)
  - total white blood cell count (WBC) outside the range of 1,500-20,000/mm^3 (1.5-20.0 x 10^9/L), only for patients taking corticosteroids
  - platelets <100,000/mm^3 (<100 x 10^9/L)
  - Hgb <8.0 g/dL
  - lymphocyte count <500/mm^3 (<0.5 X 10^9 / L)
  - neutrophil count <1500/mm^3 (<1.5 X 10^9 / L)
17. Hypoalbuminemia (serum albumin of less than 2.0 g/dL) at screening.
18. Clinical evidence of liver disease or liver injury or any of the following hepatic conditions:
  - known history of alcohol abuse, chronic liver or biliary disease
  - conjugated bilirubin greater than the upper limit of normal (ULN)
  - alkaline phosphatase (ALP) greater than 2 x ULN
  - AST (SGOT), ALT (SGPT) greater than 2 x ULN
  - gamma-glutamyl-transferase (γ -GT) greater than 2 x ULN

19. History of drug or alcohol abuse within the 12 months prior to dosing, or evidence of such abuse as indicated by the laboratory assays conducted during screening.
20. Have donated blood or experienced a loss of blood >500 mL within 4 weeks of study drug infusion.
21. Allergy to murine or human antibodies.
22. Pregnant or nursing (lactating) women, where pregnancy is defined as the state of a female after conception and until the termination of gestation, confirmed by a positive hCG laboratory test.

## 5 Restrictions for Study Subjects

Subjects must be informed and reminded of the restrictions reported in the following paragraphs.

### 5.1 Contraception requirements

Please refer to inclusion criteria ([Section 4.1](#)) for details of contraception requirements for the study. In consideration of the patient population and overall risk benefit profile, women of childbearing potential must utilize highly effective contraception to avoid becoming pregnant while receiving CFZ533 and for 12 weeks after the last dose or until data from the reproductive toxicity studies suggest otherwise.

### 5.2 Prohibited treatments

Use of the treatments in [Table 5-1](#) is not allowed during the study and until at least four weeks after the last administration of study drug.

In case of rescue therapy (IVIg or plasma exchange), study treatment should be interrupted but patient can remain in the study for the safety follow-up period or at least complete the End of Study (EoS) visit (Visit 777) assessments.

If any other prohibited treatment is given during the course of the trial, patients should be **discontinued** from the study and complete EoS visit (Visit 777) assessments as per Assessment Schedule ([Table 8-1](#)).

**Table 5-1 Prohibited treatments**

Medication	Wash-out	Action to be taken
IVIg or plasma exchange	8 weeks prior to randomisation	Investigational treatment discontinued, but patient can remain in the study for the safety follow-up period
Oral or IV cyclophosphamide; IV corticosteroid bolus (dose higher than 1 mg/kg)	3 months prior to randomisation	Patient's discontinuation and EoS assessments to be undertaken
Belimumab	6 months prior to randomisation	Patient's discontinuation and EoS assessments to be undertaken
Rituximab	12 months prior to randomisation	Patient's discontinuation and EoS assessments to be undertaken

Medication	Wash-out	Action to be taken
Any other biologic or an investigational drug	1 month or five times the half-life, whichever is longer prior to randomisation	Patient's discontinuation and EoS assessments to be undertaken
Live vaccination	4 weeks prior to randomisation	Patient's discontinuation and EoS assessments to be undertaken

Please, refer to [Section 6.10](#) for standard of care treatment instructions (e.g. corticosteroids, immunosuppressants and cholinesterase inhibitors) and other concomitant treatments.

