### 3.6 Risks and benefits

It is not known if there could be a benefit to patients from treatment with CFZ533.  
Corporate Confidential Information

Corporate Confidential Information

The risk to subjects in this trial will be minimized by adherence to the inclusion/exclusion criteria, close clinical monitoring, and targeted monitoring/follow-up visit safety assessments.

Corporate Confidential Information

Hypersensitivity or infusion reactions can manifest with itching, flushing, headache, nausea/vomiting, hypotension, urticaria, bronchospasm, or angioedema. No such events were found in the Phase 1 study with CFZ533. In this study, CFZ533 will be administered as a 2-hour infusion where such hypersensitivity reactions can still occur. Subjects will be monitored up to 4 hours after the end of the infusion at each visit.

Subjects treated with CFZ533 may be at an increased risk of infection.  
Corporate Confidential Information

Administration of CFZ533 is expected to result in immunosuppression, with a decreased capacity to mount a response to novel immunogens requiring T cell-dependent B cell activation (potentially including bacterial, viral, fungal and parasitic origin) when full receptor occupancy has been achieved.

Corporate Confidential Information

In addition, subjects will have adequate preformed antibody to maintain protective humoral response for extended periods of time (months). Subjects enrolled in this study will be carefully monitored for signs and symptoms of an infection.

Corporate Confidential Information

Although not expected in this clinical study, the investigator will monitor for signs, symptoms and laboratory results consistent with clinically significant inflammation as well as for changes in renal function and signs of acute kidney injury as per local practice.

There has been no evidence that CFZ533 has an effect on clinical coagulation parameters, and no evidence from preclinical or clinical studies that CFZ533 presents an increased risk of thromboembolic events (TE).

Corporate Confidential Information

Nevertheless, standard coagulation parameters and TEs will be carefully monitored throughout the study.

The overall risk-benefit supports further investigation in patients with autoimmune diseases such as MG patients. However, there may be unknown risks of CFZ533 which may be serious and unforeseen.

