## 6.8 Recommended treatment of adverse events

Parenteral administration of monoclonal antibodies can be associated with acute, severe reactions (occurring within the first few hours post dose) secondary to hypersensitivity, immunogenicity, or ADCC-mediated cell depletion.

In this study, CFZ533 will be administered as a 2-hour infusion. No systemic infusion reactions have been noted with CFZ533 in healthy volunteers or RA patients (Study CCFZ533X2101); however, investigators should be aware of the possibility and be prepared to treat such events.

In case of any signs of an acute reaction, clinical treatment will be provided as determined by the treating physician on a case-by-case basis and depending on the severity, using symptomatic treatment, antihistamines, NSAIDs, acetaminophen, intravenous fluids, corticosteroids, or adrenaline. Patients will be monitored at the site for at least 6 hours post dose or longer at the discretion of the Investigator to ensure adequate safety monitoring.

For the management of allergic reaction, anaphylaxis and cytokine release, it is recommended to follow the guidelines by the National Cancer Institute Common Toxicity Criteria (NCI-CTCAE/v4.03, Reference <http://evs.nci.nih.gov/ftp1/CTCAE/About.html>).

Medication used to treat AEs must be recorded on the Concomitant medications/Significant non-drug therapies CRF.

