## 7 Discontinuation and study completion

### 7.1 Discontinuation of study treatment

Patients may voluntarily discontinue the study treatment for any reason at any time.

The Investigator should discontinue study treatment for a given patient if, on balance, he/she believes that continuation would be detrimental to the subject's well-being.

- Study treatment **must** be discontinued and patients followed up for safety, if possible, if the following occur:
- In case of non-detectable AChR or MuSK autoantibodies for patients enrolled prior to this amendment.
- Significant increase in MG disease activity requiring treatment outside of a clinical trial setting.
- Worsening of MG with severe oropharyngeal or respiratory weakness (MGFA class IVb or V).
- Rescue medication use (IVIg or plasma exchange).
- Pregnancy.
- Severe or life threatening infusion reaction.
- Major worsening of renal function (e.g. >40% increase from baseline creatinine level).
- Acute infection as a severe AE as judged by the investigator.
- Major elevations (>4.0 x ULN) in amylase or lipase or any abnormal signs or symptoms suggesting pancreatic injury.
- Significant changes in standard coagulation parameters, including prothrombin time (PT), activated partial thromboplastin time (aPTT) suggesting an increased risk for hypercoagulability or any sign or symptom of a TE.
- Any other AE or complication where continued dosing of the patient is considered to be placing them at excess risk.
- Patient withdraws consent (when patient must also be withdrawn from the study).

Patients who are withdrawn from the study for any reason will not be replaced.

Study patients who discontinue participation for any reason or who decide they do not wish to participate in the study further should not be considered withdrawn from the study unless they withdraw their consent (see [Section 7.3](#)). Where possible, they should return for their EoS visit assessments (Visit 777). If they fail to return for these assessments for unknown reasons, every effort (e.g. telephone, e-mail, letter) should be made to contact them as specified in [Section 7.2.1](#). Any unresolved AEs will be followed by the investigator until resolution.

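### Sections 5.2 and 7.1 conflict on whether a patient stays in follow-up after a severe reaction or worsening MG is treated with a non-rescue prohibited drug

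*Protocol*

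**What the plan says.** Four places in the protocol bear on this.

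- **Section 5.2** deals first with rescue therapy (IVIg or plasma exchange): study drug stops, but the patient may remain for safety follow-up or at least complete the EoS visit. It then turns to everything else: "If any other prohibited treatment is given during the course of the trial, patients should be" discontinued from the study, with EoS assessments.
- **Table 5-1** lists the prohibited treatments. The entry "Oral or IV cyclophosphamide; IV corticosteroid bolus (dose higher than 1 mg/kg" carries the study-exit action. So do belimumab, rituximab, other biologics or investigational drugs, and live vaccines. No entry exempts a drug given to treat an adverse event.
- **Section 6.8** leaves treatment of an acute reaction to the physician, case by case, "using symptomatic treatment, antihistamines, NSAIDs, acetaminophen, intravenous fluids, corticosteroids, or adrenaline". It gives no dose or route and does not refer to Table 5-1.
- **Section 7.1** says study treatment must "be discontinued and patients followed up for safety, if possible, if the following occur". The listed events include "Severe or life threatening infusion reaction" and "Significant increase in MG disease activity requiring treatment outside of a clinical trial setting". It adds that patients who discontinue "should not be considered withdrawn from the study unless they withdraw their consent".

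**The concern.** A site that treats a severe infusion reaction with an IV corticosteroid bolus above 1 mg/kg acts within 6.8, must stop study drug under 7.1, and must also end the patient's participation under 5.2. Nothing says which rule prevails on participation. The same question arises for worsening MG. Under 7.1 the patient stops study drug and is followed. Under 5.2 the patient leaves if the drug chosen was rituximab, cyclophosphamide or a steroid bolus above the threshold, but may stay if it was IVIg or plasma exchange. Follow-up then depends on the local choice of drug.

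Safety throughout the study is a primary objective, and Section 3.6 states: "Administration of CFZ533 is expected to result in immunosuppression". Several of the exit-triggering drugs add further immunosuppression, so scheduled observation after them is informative.

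Efficacy is touched as well. Missing data from dropouts are not imputed (protocol 11.4.3, SAP 7.1.5). Time to first rescue counts only IVIg or plasma exchange and censors dropouts at the last visit (protocol 11.5.1, SAP 7.2.3). A patient removed because worsening was treated with another drug is therefore censored for a reason linked to outcome.

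**Working it through.** The plan states no figure for this point, so there is none to reproduce. The check is a comparison of the text, followed by a count of the scheduled time at stake.

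**Where the rules meet**

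| Situation | Section 7.1 | Section 5.2 / Table 5-1 |
|---|---|---|
| Severe or life-threatening infusion reaction, treated with an IV steroid bolus above 1 mg/kg | Study drug stops; safety follow-up if possible | Patient leaves the study after EoS |
| Same reaction, steroid by another route or at or below the threshold | Same | Not triggered |
| Worsening MG that meets 7.1, treated with IVIg or plasma exchange | Study drug stops; safety follow-up if possible | Patient may remain |
| Worsening MG that meets 7.1, treated with another prohibited drug | Study drug stops; safety follow-up if possible | Patient leaves the study after EoS |

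In the first and last rows both rules end study drug. They differ only on whether observation continues.

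**Scheduled time at stake**

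Inputs, from protocol Section 3.1: doses on Days 1, 29, 57, 85, 113 and 141; 24 weeks of treatment, then 24 weeks of follow-up.

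Planned end = 1 + (24 + 24) × 7 = Day 337. Weeks remaining at a dose = (337 − dose day) / 7.

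| Dose | Day | Weeks remaining |
|---|---|---|
| 1 | 1 | 336/7 = 48 |
| 2 | 29 | 308/7 = 44 |
| 3 | 57 | 280/7 = 40 |
| 4 | 85 | 252/7 = 36 |
| 5 | 113 | 224/7 = 32 |
| 6 | 141 | 196/7 = 28 |

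The Week 25 visit falls at about 1 + 24 × 7 = Day 169, after the last dose. An exit at any dosing day therefore comes before the primary efficacy assessment.

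**What remains after an exit under 5.2**

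- one EoS visit (5.2);
- follow-up of AEs unresolved at that point (7.1);
- reporting of all SAEs to 30 days after the last visit, and after that of SAEs suspected to be related, with progression of earlier SAEs reported whenever it occurs (9.2.2);
- new AEs that the patient believes may be related, which the patient is asked to report (9.1).

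What goes is the scheduled visits and laboratory tests, systematic collection of new non-serious AEs, later SAEs not suspected to be related, and later QMG and MGC scores.

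**How many patients**

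The documents give no rate of severe reactions, of boluses above the threshold, or of non-rescue prohibited drug use. The number affected cannot be computed.

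**The case against.** The case on the other side has real force on several points.

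- **The steroid clash is conditional.** It needs an IV bolus above 1 mg/kg and a reaction severe enough to fall under 7.1. A reader might infer that any steroid given under 6.8 removes the patient; Table 5-1 does not say that. This limit stands.
- **Section 7.1 promises less than full follow-up.** Safety follow-up is only if possible, and patients who discontinue are asked to return for EoS, the same visit that 5.2 requires. It would be wrong to read 7.1 as guaranteeing every scheduled visit. The conflict over whether the patient is still in the study remains.
- **Reporting does not stop at 30 days.** A reader might conclude that delayed events go uncaptured. Sections 7.1, 9.1 and 9.2.2 keep several routes open, and 7.2 requires follow-up care or referral for patients withdrawn early. Observation is cut short, not ended.
- **No arm imbalance is documented.** It is tempting to say that exits would come mainly from the CFZ533 arm. Section 6.8 notes that antibodies can cause acute reactions, but 3.6 and 6.8 report none with CFZ533 so far. Neither an imbalance nor a percentage of the arm can be supported.
- **The prohibition window is ambiguous.** Section 5.2 bars these drugs during the study and until at least four weeks after the last dose. If the bar lapses then, some later treatment of worsening MG would not trigger removal. Acute infusion reactions arise close to dosing and so fall inside the window on either reading.
- **Ending participation after a confounding drug is a design choice.** That is so, but IVIg and plasma exchange also confound, and those patients may remain. The choice also needs to agree with 7.1.

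Section 6.3 requires sponsor agreement on whether a patient continues after a dosing deviation. It does not exempt AE treatment from Table 5-1. The visit schedule in Table 8-1 could not be read in the text available, so the content of the EoS visit for early leavers was not checked.

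**Conclusion.** The conflict is in the text. Sections 5.2, 6.8 and 7.1 and Table 5-1 do not give one answer on the study status of two kinds of patient: one whose severe or life-threatening reaction is treated with an IV corticosteroid bolus above 1 mg/kg, and one whose worsening MG is treated with a prohibited drug other than IVIg or plasma exchange.

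If 5.2 is followed as written, each such exit on a dosing day gives up between about 28 and 48 weeks of scheduled safety and efficacy observation. This assumes removal at the time of the dose and the nominal visit calendar. An exit between doses or during follow-up gives up correspondingly less or more than the nearest dose figure.

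The point does not depend on many patients being affected, on a difference between arms, or on all later safety information being lost, and the documents establish none of these. It leaves the sample size and power unchanged. It is worth correcting because safety is a primary objective, dropouts are not imputed, and the correction is cheap.

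**What to change.** Amend the protocol so that 5.2 and Table 5-1 agree with 6.8 and 7.1:

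1. State whether a corticosteroid given under 6.8 for an acute reaction counts as a prohibited treatment.
2. Separate stopping study drug from ending data collection, so that patients who still consent can continue the safety and efficacy visits already scheduled. Record the drug and its date.
3. Clarify how long the prohibition in 5.2 lasts after the last dose.
4. In the SAP, flag data collected after a prohibited drug and say how they enter the QMG and MGC models and the time-to-rescue analysis.

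Which treatments are allowed, and when study drug stops, remain the sponsor's decision; nothing here proposes a dose or a treatment rule.

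The cost is amendment wording, a few more attendances at visits already in the schedule, and data after a confounding drug that need flagging in the analysis. No new procedure is needed.

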### **5.3 Dietary restrictions and smoking**

Subjects will maintain their usual diet and life habits during the entire study.

### **5.4 General restrictions**

No general restrictions are required in this study.

## **6 Treatment**

### **6.1 Study treatment**

#### **6.1.1 Investigational treatment**

The investigational drug (CFZ533) and placebo will be prepared by Novartis and supplied to the Investigative site as open-label bulk medication. CFZ533 will be provided as lyophilisate in vial (150 mg) and the placebo as liquid in vials.

To maintain the blind, the investigational treatments will be prepared by an unblinded pharmacist/designee and the investigational treatment will only be administered by blinded study personnel to patient treatment allocation.

Instructions for infusion preparation, storage and handling of CFZ533 vials and placebo are described in the Pharmacy Manual, provided as a separate document. Once the active or placebo will be diluted there will be no possibility to differentiate the two solutions for injection.

Study drugs must be received at the study site by a designated person, handled and stored safely and properly, and kept in a secure location to which only the Investigator and designated staff have access.

Upon receipt, the study drugs should be stored according to the instructions specified on the drug labels. Storage conditions must be adequately monitored and appropriate temperature logs maintained as source data. Appropriate documentation of the subject specific dispensing process must be maintained.

Medication labels will be in the local language, will comply with the legal requirements of each country, and will include storage conditions for the drug but no information about the patient.

All drug supplies are to be used only for this protocol and not for any other purpose. Unless specifically instructed by Novartis, the Investigator must not destroy any drug labels, or any partly used or unused drug supply. Only after receiving a written authorization by Novartis, the Investigator/designee will send all the unused and partly used drug supplies as well as the empty containers to the address provided at the time of authorization for destruction.

